1.3.2.2 Phase II studies of RAD001 in neuroendocrine tumors

A recent phase II clinical trial examined the combination of RAD001 5 mg per day and depot octreotide (Sandostatin LAR depot) in patients with advanced neuroendocrine tumors (Yao, Phan et al. 2006). Thirty patients who were treated were classified as follows: 17 patients had carcinoid, and 13 had pancreatic neuroendocrine tumor. All were evaluable for response. Four patients were reported to have partial response (3 verified by independent radiologic review), 22 had stable disease, and 4 had progressive disease by RECIST criteria. Responses appeared to be durable; at last analysis, responses were ongoing in 3 patients at 12, 9, and 6 months on treatment, and the fourth patient progressed at 9 months on treatment. A partial response to therapy was seen in 2 of 11 patients with pancreatic neuroendocrine tumor who were evaluable for response. Of the 17 patients whose tumors had documented radiological progression prior to study entry, 13 (76%) were progression-free at 12 weeks and 11 (65%) were progression-free at 24 weeks. Nineteen of the 30 evaluable patients had elevated chromogranin A at baseline. Eleven (37% of all patients or 58% of those with elevated chromogranin A at baseline) had $>50\%$ reductions in chromogranin A.

The combination of RAD001 5 mg per day and Sandostatin LAR Depot 30 mg every 28 days appears to have been well tolerated. The most common toxicity reported was mild aphthous ulceration. CTC Grade 3/4 toxicities reported included those previously reported for RAD001 alone (anemia, thrombocytopenia, aphthous ulcer, diarrhea, edema, fatigue, hypoglycemia, nausea, pain, and rash). Only one patient discontinued treatment because of drug-related toxicities. When grade 3 toxicities occurred, RAD001 was held until toxicity resolved to grade 1, and RAD001 was resumed at the initial dose of 5 mg per day.

In phase I clinical studies of RAD001 as a monotherapy agent in oncology patients, the side-effect profile is essentially mild to moderate adverse events with a low frequency of DLT at the daily dose of 10 mg/d (see Table 1-1). Based on the PK/PD model, a daily dose of 10mg RAD001 is assumed to provide a persistently high degree of target inhibition in the tumor [Investigators' Brochure-Section 5.3.1.1]. In addition, preliminary data from phase 1 studies, in which changes in molecular characteristics of tumor induced by treatment with RAD001 at the doses of 5 and 10 mg/d were investigated, confirm the pharmacodynamic activity predicted previously by PK/PD modeling [Investigators' Brochure-Section 5.3.1.1]. Therefore, a dose of 10 mg/d should ensure adequate drug target inhibition for most patients, taking into consideration the known inter-patient variability in drug levels (CV of approx 50%).

The efficacy and safety of RAD001 at a dose of 10 mg per day, alone and in combination with Sandostatin LAR, currently is being evaluated in an ongoing multi-institutional phase II clinical trial.

1.5 Study Rationale

Given the single-agent activity demonstrated with both temozolomide and RAD001 in patients with neuroendocrine tumors, evaluation of a combination of these two agents in neuroendocrine tumors is warranted. The activity of temozolomide appears to be limited primarily to patients with pancreatic neuroendocrine tumors, based on our recent clinical experience. We therefore propose a phase I/II study to evaluate the efficacy and safety of RAD001 in combination with temozolomide in patients with metastatic pancreatic neuroendocrine tumors.

Although the combination of RAD001 and gemcitabine was associated with toxicity, RAD001 has been studied in combination with paclitaxel without evidence of synergistic toxicity. This data, as well as the markedly different mechanisms of action of RAD001 and temozolomide, suggest that combining these two agents at standard doses, with appropriate safety monitoring, may be feasible. However, to ensure that we do not miss unexpected toxicities, we will initiate treatment at a dose level below the anticipated phase II dose. Three patients will be treated with RAD001 orally at a dose of 5 mg daily, in combination with temozolomide at a standard dose (150 mg/m² daily for 7 days, followed by a 1 week break). Patients will be observed for toxicity. If no dose limiting toxicity is observed in this first cohort, subsequent patients will receive the full anticipated phase II dose of RAD001 10 mg daily, in combination with temozolomide 150 mg/m² daily for 7 days, every other week. To minimize the risk of lymphopenia-related opportunistic infections, temozolomide therapy will be limited to a maximum of 6 months, and all patients will receive PCP prophylaxis.

2 Study objectives

Primary

- To determine the objective response rate of RAD001 in combination with temozolomide in patients with advanced (unresectable or metastatic) pancreatic neuroendocrine tumors.

Secondary

- To determine the duration of response to the combination of RAD001 and temozolomide in patients with advanced pancreatic neuroendocrine tumors.
- To determine the safety and tolerability of the combination of RAD001 and temozolomide in patients with advanced pancreatic neuroendocrine tumors.
- To determine the progression free survival and overall survival of patients receiving the combination of RAD001 and temozolomide.

3 Investigational plan

3.1 Overall study design

This is an open-label phase I/II study to evaluate the efficacy and safety of RAD001 in combination with temozolomide in patients with advanced pancreatic neuroendocrine tumor.

Patients on study therapy may be at risk for temozolomide-related selective lymphopenia and opportunistic infections. To reduce the risk of opportunistic infections, patients will receive prophylaxis with Bactrim DS, 1 tablet by mouth every Monday, Wednesday, and Friday beginning after the first month of treatment. Patients allergic to Bactrim should be initiated on an alternate, standard PCP prophylaxis regimen. Previous infections associated with temozolomide-induced lymphopenia in neuroendocrine tumor patients have developed after more than 6 months of treatment. Treatment with temozolomide in this study will therefore be limited to a maximum duration of 6 months.

3.2 Basic Design Characteristics

Up to 44 patients with locally advanced or metastatic pancreatic neuroendocrine tumors who meet eligibility criteria will be enrolled sequentially into three cohorts.

3.2.1 Cohort 1

The first cohort will consist of a minimum of three patients who will receive an oral dose of 5 mg of RAD001 administered daily and an oral dose of temozolomide of 150 mg/m² daily for

7 days every other week beginning on Day 1 of RAD001 administration. The patients will be treated for a 28-day Treatment Period and then observed over a 7-day observation period for signs of treatment-emergent toxicity. Patients will not receive treatment with either RAD001 or temozolomide during the 7-day observation period. If these patients do not exhibit disease progression or a dose limiting toxicity (DLT), as defined in section 3.3, they will receive subsequent 28-day cycles of treatment without additional 7-day observation periods. Patients in this cohort may be treated simultaneously without requiring previously enrolled patients to complete their first cycle of treatment and observation.

If a dose limiting toxicity (DLT), as defined in section 3.3, is observed in 1 of the first 3 patients, 3 additional patients will be enrolled at that same dose level. If no additional DLT is observed after all patients have completed the first cycle of treatment and 7-day observation period, the trial will continue to enroll the second cohort of patients.

If a DLT is observed in 2 or more of the first 3 patients or of the total 6 patients during Cycle 1 of treatment, accrual to the trial will be suspended pending review of the events and revision of the protocol.

3.2.2 Cohort 2

Once the first cohort of patients completes the initial 35-day cycle without experiencing a DLT, the second cohort of patients will begin enrollment. The second patient cohort will consist of at least 3 patients who will receive an oral dose of 10 mg of RAD001 administered daily and an oral dose of temozolomide of 150 mg/m² daily for 7 days every other week beginning on Day 1 of RAD001 administration. The patients will be treated for a 28-day Treatment Period and then observed over a 7-day observation period for signs of treatment-emergent toxicity. Patients will not receive treatment with either RAD001 or temozolomide during the 7-day observation period. If patients do not exhibit disease progression or a dose limiting toxicity (DLT), as defined in section 3.3, they will receive subsequent 28-day cycles of treatment without additional 7-day observation periods. Patients in this cohort may be treated simultaneously without requiring previously enrolled patients to complete their first cycle of treatment and observation.

If a DLT is observed in 1 of the first 3 patients, 3 additional patients will be enrolled at that same dose level. If no additional DLT is observed after all patients have completed the first cycle of treatment and observation period, the trial will continue to enroll the third cohort of patients. If additional DLTs are observed, enrollment to the trial will be stopped and the study will be re-evaluated.

If a DLT is observed in 2 or more of the first 3 patients or of the total 6 patients during Cycle 1 of treatment, accrual to the trial will be suspended pending review of the events and revision of the protocol.

3.2.3 Cohort 3

Once the second cohort of patients completes the initial 35-day cycle without experiencing a DLT, the third cohort of patients will begin enrollment. The third patient cohort will consist of 32 patients who will receive an oral dose of the maximum tolerated dose of RAD001 administered daily and an oral dose of temozolomide of 150 mg/m² daily for 7 days every other week beginning on Day 1 of RAD001 administration. The patients will be treated for a 28-day Treatment Period. Patients who complete the initial cycle of therapy without evidence of significant treatment-emergent toxicity or progressive disease may receive additional 28-day cycles of treatment until the appearance of significant treatment-emergent toxicities or disease progression.

3.3 Definition of dose limiting toxicity (DLT) and maximum tolerated dose (MTD)

Dose limiting toxicity is defined as drug-related toxicity according to the NCI CTCAE v3.0 during the first cycle of treatment leading to the following:

- Grade 3 or higher non-hematologic toxicity (excluding nausea and/or vomiting).
- Grade 3 or higher nausea/vomiting uncontrolled by aggressive antiemetic support.
- Grade 3 or higher neutropenia or thrombocytopenia failing to revert to grade ≤ 2 (level at which cytotoxic treatment is permitted) in three weeks
- Febrile neutropenia
- Inability of the patient to take $> 75\%$ of the planned chemotherapy dose during the treatment period.
- Clinically significant treatment related toxicity

The maximum tolerated dose (MTD) is defined as the highest dose level at which less than 33% of the patients experience a DLT.

If a DLT is observed in 2 or more of the first 3 patients or of the total 6 patients in a dose level during cycle 1 of treatment, that dose level will be considered to be above the maximum tolerated dose (MTD). The dose one level lower will be declared as the MTD, if a DLT is observed in 1 or less patient of the total 6 patients in the dose level. If 2 or more patients have experienced a DLT at the first dose level, the investigator, medical monitor, and Sponsor may discuss to add a dose level at 50% of the first level.

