Metabolic changes (hyperlipidemia and hyperglycemia) may be observed during treatment with RAD001. Both events may be medically managed. Hyperlipidemia has been reported as an adverse reaction in 10% of patients although review of the laboratory values suggests that as many as a quarter of patients develop grade 1-2 hyperlipidemia on treatment, mostly hypercholesterolemia. Hyperglycemia has been reported as an adverse event in 7% of patients. Grade 3 hyperglycemia has been observed, especially in diabetics receiving RAD001 treatment. Therefore, patients with diabetes should have their blood glucose monitored carefully and their medications adjusted, as needed, to maintain adequate control of their blood glucose levels.

In Novartis-sponsored clinical trials, symptomatic non-infectious pneumonitis has been reported as a serious adverse event in less than 1% of patients out of approximately 1000 cancer patients treated with RAD001 as of April 30, 2006. This adverse event has been noted in the Investigators' Brochure (IB, Edition 4 dated November 11, 2005). Corticosteroids were often administered to the patients with symptomatic pneumonitis.

Novartis has recently received reports of low-grade non-infectious pneumonitis in cancer patients treated with RAD001. Most of these reports involve patients with no respiratory symptoms (CTC grade 1 pneumonitis: radiographic findings only) or mild severity (CTC grade 2: symptomatic, not interfering activities of daily living), and were from two investigator-sponsored (private IND) trials, as follows:

- In a study of patients with advanced renal cell carcinoma receiving 10 p.o. mg/day, 15/20 patients reviewed by an independent radiologist were noted to have lung infiltrates consistent with pneumonitis on routine chest CT scans performed to follow the patients' thoracic metastases.
- In a study of patients with advanced breast cancer, 7/18 patients treated with RAD001 10 mg/d and 2/16 patients treated with RAD001 70 mg/week, had findings consistent with pneumonitis. In this study, two patients, one on the daily RAD arm and one on the weekly RAD001 arm, developed severe (grade 3) pneumonitis that resolved after RAD001 was discontinued.

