4.4.4 Dose reductions for non-hematologic toxicity

Both RAD001 and temozolomide should be held for all clinically significant drug related toxicities that are grade 3 or higher and not specified in the drug-specific toxicities below. All drug related CTCAE Grade 3 and 4 toxicities must have resolved to at least CTCAE Grade 1 prior to repeat dosing. For patients with baseline grade 2 elevations in transaminases or bilirubin or alkaline phosphatase, transaminase, bilirubin, or alkaline phosphatase levels must have resolved to the level defined by the Inclusion Criteria prior to repeat dosing.

Once toxicities have resolved to at least grade 1, RAD001 and temozolomide will be reinitiated at one reduced dose level per Table 4.3. If treatment is held more than 3 weeks, the patient should be taken off protocol therapy.

If multiple toxicities are seen, the dose administered should be based on the dose reduction required for the most severe grade of any single toxicity observed. If unacceptable toxicity occurs, therapy should be discontinued.

Table 4.3 Criteria for dose-modification of RAD001 and temozolomide for non-hematologic toxicity

Toxicity	Actions
Grade 2 (except pneumonitis [refer to Table 4.4] and mucositis)	If the toxicity is tolerable to the patient, maintain the same dose. If the toxicity is intolerable to patient, interrupt RAD001 and temozolomide until recovery to grade ≤ 1 . Then reintroduce RAD001 and temozolomide at one lower dose level.
Grade 2 mucositis	If the toxicity is tolerable to the patient, maintain the same dose. If the toxicity is intolerable to patient, interrupt RAD001 and temozolomide until recovery to grade ≤ 1 . Then reintroduce RAD001 at one lower dose level and continue same dose of temozolomide. See section 4.4.5 for further details.
Grade 3 (except hyperlipidemia and hyperglycemia and mucositis and pneumonitis)	Interrupt RAD001 and temozolomide until recovery to grade ≤ 1 . Then reintroduce both RAD001 and temozolomide at one lower dose level.
Grade 3 hyperlipidemia	Grade 3 hyperlipidemia (hypercholesterolemia and/or hypertriglyceridemia) should be managed using medical therapies, per section 4.4.6. Dose reduction of RAD001 or temozolomide can be considered but is not required.
Grade 3 hyperglycemia	Grade 3 hyperglycemia should be managed using medical therapies, per section 4.4.6. Dose reduction of RAD001 or temozolomide can be considered but is not required.

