4.4.6 Management of hyperlipidemia and hyperglycemia

Treatment of *hyperlipidemia* is recommended but not required as part of study therapy, and should take into account the patient's underlying condition and the relative risk/benefit ratio of treatment. Treatment of hyperlipidemia should take into account the pre-treatment status and dietary habits. For patients with grade 2 hypercholesterolemia (>300 mg/dL or 7.75 mmol/L) or grade 2 hypertriglyceridemia (>2.5 x upper normal limit) consideration should be given to treatment with a statin or appropriate lipid-lowering medication, in addition to diet. Patients should be monitored clinically and through serum biochemistry for the development of rhabdomyolysis and other adverse events as required in the product label/data sheets for HMG-CoA reductase inhibitors.

Note: Concomitant therapy with fibrates and an HMG-CoA reductase inhibitor is associated with an increased risk of a rare but serious skeletal muscle toxicity manifested by rhabdomyolysis, markedly elevated creatine kinase (CPK) levels and myoglobinuria, acute

renal failure and sometimes death. The risk versus benefit of using this therapy should be determined for individual patients based on their risk of cardiovascular complications of hyperlipidemia.

Grade 3 *hyperglycemia* has been observed in patients receiving RAD001 therapy. In almost all cases the affected patients had an abnormal fasting glucose at baseline. Based on this finding, we suggest that optimal glucose control should be achieved before starting a patient on RAD001 and should be monitored during RAD001 therapy. For patients who develop clinically significant hyperglycemia while on therapy, initiation of oral hypoglycemic or insulin therapy should be considered.

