5.1.2 Evaluations during treatment

5.1.2.1 Day 1 of every cycle

- Physical examination
- Toxicity assessment
- Vital signs
- Weight
- Serum chemistries

- CBC with differential

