5.1.2.2 Day 15 of cycles 1 through 6 only

- Physical examination
- Toxicity assessment
- Vital signs
- Weight
- CBC with differential

5.1.2.3 Data to be obtained following every 2 cycles of treatment (time of restaging):

- Radiologic assessment of tumor burden by CT scan
- Assessment of serum chromogranin A and other secretory proteins (if applicable).

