7.1 Adverse events

Information about all adverse events, whether volunteered by the subject, discovered by investigator questioning, or detected through physical examination, laboratory test or other means, will be collected and recorded and followed as appropriate.

An adverse event is the appearance or worsening of any undesirable sign, symptom, or medical condition occurring after starting the study drug even if the event is not considered to be related to study drug. Medical conditions/diseases present before starting study drug are only considered adverse events if they worsen after starting study drug. Abnormal laboratory values or test results constitute adverse events only if they induce clinical signs or symptoms, are considered clinically significant, or require therapy.

The occurrence of adverse events should be sought by non-directive questioning of the patient at each visit during the study. Adverse events also may be detected when they are volunteered by the patient during or between visits or through physical examination, laboratory test, or other assessments. As far as possible, each adverse event should be evaluated to determine:

1. the severity grade (mild, moderate, severe) or (grade 1-4)
2. its relationship to the study drug(s) (suspected/not suspected)
3. its duration (start and end dates or if continuing at final exam)
4. action taken (no action taken; study drug dosage adjusted/temporarily interrupted; study drug permanently discontinued due to this adverse event; concomitant medication taken; non-drug therapy given; hospitalization/prolonged hospitalization)
5. whether it constitutes a serious adverse event (SAE)

All adverse events should be treated appropriately. Such treatment may include changes in study drug treatment including possible interruption or discontinuation, starting or stopping concomitant treatments, changes in the frequency or nature of assessments, hospitalization, or any other medically required intervention. Once an adverse event is detected, it should be followed until its resolution, and assessment should be made at each visit (or more frequently, if necessary) of any changes in severity, the suspected relationship to the study drug, the interventions required to treat it, and the outcome.

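### In Cohorts 1 and 2 no serum chemistry is scheduled while patients are on drug in Cycle 1, and the next cohort can open before the first post-dose panel is reviewed

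*Combined protocol and SAP*

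**What the plan says.** **What counts.** Section 3.3 limits DLTs to drug-related toxicity in the first cycle. One criterion is "Grade 3 or higher non-hematologic toxicity (excluding nausea and/or vomiting"), with no duration condition. Section 7.1 narrows this for laboratory findings: "Abnormal laboratory values or test results constitute adverse events only if they induce clinical signs or symptoms, are considered clinically significant, or require therapy".

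**How chemistry toxicity is handled.** Section 4.4.4, Table 4.3, says "Grade 3 hyperglycemia should be managed using medical therapies, per section 4.4.6" and leaves dose reduction optional. For other clinically significant drug-related toxicity of Grade 3 or more, the same section holds both drugs and adds: "All drug related CTCAE Grade 3 and 4 toxicities must have resolved to at least CTCAE Grade 1 prior to repeat dosing". It has a separate resumption rule for patients whose transaminases, bilirubin or alkaline phosphatase were Grade 2 at baseline.

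**When chemistry is drawn.** The visit headed "Day 1 of every cycle" (5.1.2.1) includes serum chemistries and a CBC. The visit headed "Day 15 of cycles 1 through 6 only" (5.1.2.2) includes a CBC but no chemistry. Table 5.1 agrees, and lets screening results stand in for Cycle 1 Day 1. Section 7 allows two days either side of each scheduled assessment.

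**How the next cohort opens.** In Cohorts 1 and 2, Cycle 1 is 28 days of treatment plus 7 days off both drugs (3.2.1, 3.2.2). Sections 3.2.2 and 3.2.3 open the next cohort when the previous one finishes the 35-day cycle without a DLT. They name no laboratory review.

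**The concern.** The DLT definition reaches chemistry abnormalities, but the schedule does not look for them during the exposure that it is meant to judge. Whether a value is clinically significant or needs treatment cannot be decided if the value is never obtained. The protocol itself reports a relevant signal for RAD001: "Grade 3 hyperglycemia has been observed, especially in diabetics receiving RAD001 treatment" (1.3.2.1).

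The move to 10 mg, the MTD and the dose for the 32 patients of Cohort 3 rest on DLT counts in 3-6 patients per level. An event that is never sampled is recorded as no DLT, so the error can run in one direction only: it makes a dose level look safer. Later chemistry and the quarterly DSMC review (12.2) may reveal the toxicity. By then the cohort-opening decision may have been taken, and events after Cycle 1 fall outside the 3.3 definition.

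**Working it through.** The plan states no operating characteristic for the DLT rule, so there is no figure to reproduce. The check is a calendar built from 3.2, 5.1.2, Table 5.1 and the Section 7 window.

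**Calendar, Cohorts 1 and 2**
- Cycle 1 = 28 + 7 = 35 days, so Cycle 2 Day 1 = Day 36, or Days 34-38 with the window.
- Scheduled chemistry panels on Days 2-28: 0. On Days 29-35: 0 on the nominal schedule.
- Last RAD001 dose is Day 28, so the first panel comes 34 − 28 = 6 to 38 − 28 = 10 days later. Last temozolomide dose is Day 21, which is 36 − 21 = 15 days before nominal Day 36.
- With the 30-hour terminal half-life in 4.5.1.2, and assuming simple exponential decline, the RAD001 remaining on Day 36 is 0.5^(192/30) = 1.2% (3.6% on Day 34, 0.4% on Day 38).
- The first scheduled panel on continuous RAD001 is Cycle 3 Day 1 = 36 + 28 = Day 64. Cohort 3 has no drug-free week, so its first is Day 29.

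**Which episodes the calendar can miss.** Durations are not in the documents, so L below is an assumption. An episode of L days starting on Day s (s = 2 to 28, 27 possible days) is missed if no panel day c satisfies s ≤ c < s + L. With Day 36 as the only panel, it is missed when s ≤ 36 − L.

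| Assumed L (days) | Missed, Day 36 only | of which over by Day 28 | of which ending Days 29-35 | Missed, Days 15 + 36 | Missed, Days 15 + 25 + 36 |
|---|---|---|---|---|---|
| 7 | 27 | 21 | 6 | 20 | 13 |
| 10 | 25 | 18 | 7 | 15 | 5 |
| 14 | 21 | 14 | 7 | 7 | 0 |
| 21 | 14 | 7 | 7 | 0 | 0 |
| 28 | 7 | 0 | 7 | 0 | 0 |
| 35 | 0 | 0 | 0 | 0 | 0 |

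If the panel is drawn on Day 34, the first results column becomes 26, 23, 19, 12, 5, 0. On Day 38 it becomes 27, 27, 23, 16, 9, 2.

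These are counts of onset days, not of patients or DLTs. The column for episodes ending on Days 29-35 matters most, because those are abnormalities that clear once the drugs stop. For L = 21 and 28 their onsets are Days 9-15 and 2-8, and a Day 15 panel catches them all. For L = 7, 10 and 14 their onsets are Days 23-28, 20-26 and 16-22, all after Day 15. Only a draw near the end of dosing reaches these.

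**Cohort opening.** Nominal Day 36 falls one day after the Day 35 trigger. The window allows a draw on Day 34 or 35, but nothing requires it.

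**The case against.** The strongest reply is that few of these onset days are credible dose-limiting events. To be missed, an abnormality must be symptomless, not otherwise tested, and gone by the panel day. For the shorter assumed durations most misses end while dosing continues (14 of 21 at L = 14), and under 7.1 such a value would count essentially only if judged clinically significant. This stands, and it limits the weight of the table.

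On glucose, the plan leaves dose reduction for Grade 3 hyperglycemia optional, and 4.4.6 notes that nearly all those affected had abnormal fasting glucose beforehand. It also advises that "optimal glucose control should be achieved before starting a patient on RAD001 and should be monitored during RAD001 therapy". This is a real partial safeguard, but it carries no dates and does not cover liver or renal tests. The Day 15 toxicity assessment and continuous AE collection should catch symptomatic events, and unscheduled tests are not barred.

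On cohort opening, the nominal gap is one day, new patients must still be consented and registered (Section 11), and with staggered entry some Day 36 results will already be known. Case report forms are due within 10 days of cycle end (12.1.2), and Appendix B, 7.0, has toxicities recorded before each course. None of these is tied to opening a cohort.

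Two stronger readings are tempting. A reader might infer that prolonged cytopenias are missed too. They are not: the CBC is drawn on Days 15 and 36, and no run of 21 days or more starting on Days 2-36 avoids both. A reader might also put an assumed unsampled share into the 3+3 rule and quote the chance that a toxic dose passes. The documents offer no basis for such a share. They report hyperglycemia as an adverse event in 7% of patients, not restricted to Grade 3 (1.3.2.1), and few DLTs at 10 mg daily in monotherapy (1.3.2.2).

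**Conclusion.** The gap is real and modest. The calendar facts are certain: no scheduled chemistry on Days 2-28, a first panel 6-10 days after RAD001 stops, and no required review of it before the next cohort opens. What can be lost is a symptomless, drug-related Grade 3 or higher chemistry abnormality that would have been judged clinically significant or needed therapy, and that reverses on or off drug before the Cycle 2 Day 1 draw. Persistent events will be measured at that draw, although possibly after the next cohort has opened.

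The effect on the DLT count has a known direction (undercounting) and an unknown size. The onset-day counts rest on assumed durations, visits on the stated days and no unscheduled testing. The documents do not support the inference that the MTD will be set too high, or that any particular fraction of DLTs will be lost. The point is worth acting on because each level is judged on 3-6 patients and the remedy is cheap.

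**What to change.** For Cohorts 1 and 2 only:

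1. Add fasting serum chemistry to the existing Cycle 1 Day 15 blood draw in 5.1.2.2 and Table 5.1. Optionally add one panel near the end of dosing (about Days 22-28), which is the draw that reaches short, late-onset episodes.
2. State in 3.2 that the pre-dose Cycle 2 Day 1 CBC and chemistry of every patient in the cohort are reviewed for DLT before the next cohort opens, and that a drug-related abnormality found there counts as a Cycle 1 event. The second clause has to be written out, because 3.3 otherwise confines DLTs to the first cycle.

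Doses, treatment schedule and toxicity grades stay as they are. The cost is a short amendment, one added panel on an existing draw and at most one extra draw in 6-12 patients, and a wait of a day or so for the Cycle 2 Day 1 results.
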